# 7 **BONE FRACTURES**

Adverse events related to bone fractures will be identified by searching for any PT including the text string 'fracture' excluding 'tooth fracture'

# 8 PANCREATITIS

Adverse events related to pancreatitis will be identified using the following PTs:

Cullen's sign

Hereditary pancreatitis

Ischaemic pancreatitis

Oedematous pancreatitis

Pancreatic abscess

Pancreatic haemorrhage

Pancreatic necrosis

Pancreatic phlegmon

Pancreatic pseudocyst

Pancreatic pseudocyst drainage

Pancreatitis

Pancreatitis acute

Pancreatitis chronic

Clinical Study Protocol Appendix I Drug Substance Saxagliptin Study Code D1680C00003 Edition Number 2.0 Date Pancreatitis haemorrhagic

Pancreatitis necrotising

Pancreatitis relapsing

Pancreatorenal syndrome

# 9 SKIN REACTIONS

Adverse events related to skin reactions will be identified using the following PTs:

Anal erosion

Anal ulcer

Anal ulcer haemorrhage

Anorectal ulcer

Auditory meatus external erosion

Diabetic neuropathic ulcer

Diabetic ulcer

Epidermal necrosis

Eyelid erosion

Fungating wound

Genital erosion

Genital ulceration

Infected skin ulcer

Lip erosion

Lip ulceration

Nasal necrosis

Nasal septum ulceration

Nasal ulcer

Clinical Study Protocol Appendix I Drug Substance Saxagliptin Study Code D1680C00003 Edition Number 2.0 Date
Neuropathic ulcer
Nipple ulceration
Penile necrosis
Penile ulceration
Scab
Scrotal ulcer
Skin erosion
Skin necrosis
Skin ulcer
Skin ulcer excision
Skin ulcer haemorrhage
Testicular necrosis
Vulval ulceration
Vulvar erosion
Vulvovaginal ulceration

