# 2.3 Safety objectives

#### 2.3.1 Secondary safety objectives

Safety and tolerability will be evaluated by assessment of overall AEs and AEs of special interest. These will include assessment of the long-term effects of saxagliptin on decrease in lymphocyte counts, decrease in thrombocyte counts, severe infections, hypersensitivity reactions, liver abnormalities, bone fractures, pancreatitis, skin reactions and renal abnormalities. See Appendix I for information on identification of these events.

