#### 6.4.2 Definition of serious adverse event

An SAE is an AE occurring during any study period (ie, treatment, follow-up) and at any dose of the IPs (including placebo) that fulfils 1 or more of the following criteria:

- Results in death
- Is immediately life-threatening
- Requires in-patient hospitalisation or prolongation of existing hospitalisation
- Results in persistent or significant disability or incapacity
- Is a congenital abnormality or birth defect
- Is an important medical event that may jeopardise the patient or may require medical intervention to prevent one of the outcomes listed above

In addition, the following events (regardless of whether or not they meet any of the serious criteria above) will be collected as SAEs:

- Cancer
- Drug dependency/abuse

For the purposes of regulatory reporting, the following events/medical concepts should be transmitted as described in Section 6.4.4 in the same timelines as SAEs.

- Pancreatitis
- Opportunistic infections (eg, tuberculosis, Herpes zoster, cytomegalovirus, *Pneumocystis jirovecii*, etc)
- Serum AST or ALT greater than or equal to 3 times ULN, and serum TB greater than 2 times ULN or evidence of jaundice.
- Angioedema
- Anaphylaxis

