#### • Steven Johnson syndrome

For further guidance on the definition of an SAE, see Appendix B.

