# **5 HYPERSENSITIVITY REACTIONS**

Hypersensitivity adverse events will be identified using the following MedDRA PTs:

Allergic oedema

Anaphylactic reaction

Anaphylactic shock

Anaphylactoid reaction

Anaphylactoid shock

Angioedema

Auricular swelling

Bronchial oedema

Circumoral oedema

Conjunctival oedema

Drug hypersensitivity

Endotracheal intubation

Epiglottic oedema

Eye oedema

Eye swelling

Eyelid oedema

Face oedema

Gastrointestinal oedema

Genital swelling

Gingival oedema

Gingival swelling

Gleich's syndrome

Hereditary angioedema

Hypersensitivity

Idiopathic urticaria

Intubation

Laryngeal dyspnoea

Laryngeal obstruction

Laryngeal oedema

Laryngospasm

Laryngotracheal oedema

Lip oedema

Lip swelling

Nasal oedema

Oedema genital

Oedema mouth

Oedema mucosal

Oral allergy syndrome

Orbital oedema

Oropharyngeal spasm

Oropharyngeal swelling

Palatal oedema

Penile oedema

Penile swelling

Periorbital oedema

Pharyngeal oedema

Scrotal oedema

Scrotal swelling

Small bowel angioedema

Stridor

Swelling face

Swollen tongue

Throat tightness

Tongue oedema

Tracheal obstruction

Tracheal oedema

Tracheostomy

Type I hypersensitivity

Urticaria

Urticaria cholinergic

Urticaria chronic

Urticaria papular

Vaginal oedema

Vaginal swelling

Visceral oedema

Vulval oedema

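### Appendix I gives Stevens-Johnson syndrome no event-of-special-interest category, although Section 6.4.2 singles it out, and it lets three airway-procedure terms count as hypersensitivity on their own

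*Protocol*

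**What the plan says.** Section 2.3.1 makes the events of special interest part of the secondary safety objectives and points to the appendix for their definition: "hypersensitivity reactions, liver abnormalities, bone fractures, pancreatitis, skin reactions and renal abnormalities. See Appendix I for information on identification of these events".

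Appendix I, section 9, then fixes the skin category by a list: "Adverse events related to skin reactions will be identified using the following PTs". Section 5 of the same appendix does so for hypersensitivity: "Hypersensitivity adverse events will be identified using the following MedDRA PTs". That second list includes "Endotracheal intubation", a separate entry for intubation, and "Tracheostomy".

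Section 6.4.2 of the main protocol names a short set of events that "should be transmitted as described in Section 6.4.4 in the same timelines as SAEs". The last of them is "Steven Johnson syndrome".

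**The concern.** Two separate features of the term lists are at issue.

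- **Omission.** An event that the protocol considers important enough for rapid transmission has no category in the appendix that defines events of special interest. If the lists are applied as written, a case coded only as Stevens-Johnson syndrome is counted neither under skin reactions nor under hypersensitivity.
- **Over-inclusion.** Three terms in the hypersensitivity list name airway procedures, not reactions. The trial enrols patients with established cardiovascular disease or multiple risk factors and expects to run for 4-5 years. Some patients could be intubated for reasons unrelated to allergy, such as cardiac arrest or surgery. If the procedure itself is coded as an adverse event, it counts as hypersensitivity.

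At stake is how well two between-arm safety summaries reflect what their labels say.

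**Working it through.** No formula in the plan is involved, so the check is a reading of the lists against each other.

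**Step 1. Section 6.4.2 against Appendix I.** The events to be sent on SAE timelines, and where each is covered:

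| Event in Section 6.4.2 | Place in Appendix I |
|---|---|
| Pancreatitis | Section 8 |
| Opportunistic infections | Section 4 |
| Transaminase rise with raised bilirubin or jaundice | Section 6 |
| Angioedema | Section 5, under that term |
| Anaphylaxis | Section 5, as anaphylactic reaction and anaphylactic shock |
| Stevens-Johnson syndrome | None |

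Five of the six have a category; one has none.

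**Step 2. Term counts.** Counted by reading, section 9 holds 33 skin terms and section 5 holds 66 hypersensitivity terms. Stevens-Johnson syndrome is 0 of 33 and 0 of 66, and no other Appendix I list names it. The nearest skin entry is "Epidermal necrosis", which is a different preferred term. A case coded that way would be counted; a case coded as the syndrome would not.

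**Step 3. Procedure terms.** Of the 66 hypersensitivity terms, 3 are airway procedures, leaving 66 - 3 = 63 others. Section 5 attaches no condition to the three. Appendix I does use conditions elsewhere. Section 3 requires a serious infection to meet both of two criteria. The adverse-event criterion in section 6 requires one term from each of two columns.

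**Step 4. Direction and size.** Let p be the placebo proportion with true hypersensitivity, RR the true risk ratio, and q the proportion per arm counted only because of an unrelated procedure term, assumed equal in both arms. The observed ratio is

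(RR × p + q) / (p + q).

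This equals RR when q = 0 and moves towards 1 as q grows relative to p. The protocol gives neither p nor q, so the direction of any dilution is known but its size is not. No frequency is given for Stevens-Johnson syndrome either.

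**The case against.** The case for leaving the lists alone has real weight.

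- **The skin list has a coherent scope.** Its entries all concern ulceration, erosion, necrosis, wounds or scabs. The protocol nowhere says that the category is meant to hold severe drug eruptions. This stands, and it means the omission may be a matter of scope. It does not explain why the syndrome is also missing from hypersensitivity and from every other list.
- **Section 6.4.2 serves regulatory reporting, and the two lists were not built to match.** For instance, Section 6.4.2 names herpes zoster without qualification, while Appendix I takes only disseminated, neurological or multidermatomal forms. This also stands: the fault is a lack of reconciliation between two passages.
- **No case is lost.** The syndrome remains an adverse event, goes out on SAE timelines, and enters the overall adverse-event summary by arm (Sections 12.1.3.5 and 12.2.2). That is correct and limits the harm. It does not place the case in a special-interest summary.
- **Stand-alone procedure terms should be uncommon.** Section 6.4.1 defines an adverse event as a medical condition, Section 6.4.3 prefers diagnoses, and Section 6.4.4.2 sends suspected cardiovascular endpoints to their own case report form modules. Appendix B mentions intubation as a marker of angioedema severity, so the three terms may be a deliberately sensitive search. This reduces the expected number but does not make it zero, and a sensitive search can be kept while its yield is shown separately.
- **The definitions may be updated.** Appendix I, section 1, says so in a sentence about the MedDRA version. That permits a correction but does not make one.

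A reader might infer that two secondary safety results will be misclassified, or that a true hypersensitivity signal would be diluted by a definite amount. The documents support neither. Whether any case is affected depends on how events are coded, and a figure for dilution would rest wholly on invented frequencies.

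**Conclusion.** The point holds as a minor definitional one. Appendix I is not reconciled with Section 6.4.2 on Stevens-Johnson syndrome, and a case coded only under that term would be left out of both the skin and the hypersensitivity summaries. Three unconditioned airway-procedure terms mean that some non-allergic events could be counted as hypersensitivity.

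The size cannot be stated from the documents and is probably small. The conclusion assumes that the lists are applied exactly as written and, for the second part, that at least some procedures are coded as adverse events in their own right. Safety variables other than the primary composite are summarised descriptively, with no test or margin attached to these events, so the primary and confirmatory secondary analyses are untouched.

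**What to change.** Before unblinding, edit Appendix I in two places.

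1. Give Stevens-Johnson syndrome a category, preferably reported as its own line. Adding it to section 9 would pool it with terms such as diabetic ulcer and skin ulcer, where a single case would be hard to see.
2. Count the three airway-procedure terms as hypersensitivity only when another term from the section 5 list is reported for the same episode, following the paired pattern of sections 3 and 6, or show them on a separate line.

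The cost is a short edit with no new data collection. Section 6.4.3 already records start and stop dates for each adverse event, which is enough to define an episode. The downside is that an allergic reaction recorded only as an airway procedure would leave the main hypersensitivity count. A separate line for those terms would still show it.

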# 10 RENAL ABNORMALITIES

Renal abnormalities are identified by:

Doubling of creatinine levels

Development of end-stage renal disease (eg, dialysis or renal transplantation)

And/or by the following PTs covering acute renal failure:

Acute prerenal failure

Anuria

Azotaemia

Continuous haemodiafiltration

Haemodialysis

Nephropathy toxic

Oliguria

Peritoneal dialysis

Renal failure

Renal failure acute

Renal impairment

Renal transplantation
